6.5 CONCOMITANT THERAPY

Any medication or vaccine (including over-the-counter or prescription medicines, vitamins, and/or herbal supplements) that the participant is receiving at the time of enrollment or receives during the study must be recorded along with:

- Reason for use.
- Dates of administration including start and end dates.
- Dosage information including dose and frequency.

During the study, the following medications are prohibited.

- Any glucose-lowering agents other than:
 - the IMP (Toujeo or Tresiba),
 - the patient's current background basal insulin analog during the run-in period (which may not be changed during the study),
 - the patient's existing mealtime insulin (which may not be changed during the study).

This includes oral or injectable glucose lowering agents, other type of basal insulin (eg, NPH), pre-mixed insulin, and human regular insulin,

- Insulin pump therapy is not allowed during the course of the study.
- Initiation of any weight loss drugs is not allowed; previous treatment with weight loss drugs can be continued and doses must remain stable throughout the study.
- Systemic glucocorticoids for more than 10 consecutive days (topical or inhaled applications are allowed).

Other medications which are unlikely to interfere with the IMP and the study variables are allowed as needed and discussed with the Investigator. However, doses of chronically administered medicines should be kept fixed during the trial if at all possible.

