7 DISCONTINUATION OF STUDY INTERVENTION AND PARTICIPANT DISCONTINUATION/WITHDRAWAL

7.1 DISCONTINUATION OF STUDY INTERVENTION

7.1.1 Definitive discontinuation

The IMP should be continued whenever possible.

In case the IMP is stopped, it should be determined whether the stop can be made temporarily; definitive IMP discontinuation should be a last resort. Any IMP discontinuation must be fully documented in the eCRF. In any case, the participant should remain in the study as long as possible.

Definitive intervention discontinuation is any intervention discontinuation associated with the definitive decision from the Investigator not to re-expose the participant to the IMP at any time during the study, or from the participant not to be re-exposed to the IMP whatever the reason.

List of criteria for permanent treatment discontinuation

The patients may withdraw from treatment with the IMP if they decide to do so, at any time and irrespective of the reason, or this may be the Investigator's decision. All efforts should be made to document the reason(s) for treatment discontinuation and this should be documented in the eCRF.

The patients may withdraw from treatment with IMP in case of the following:

- At patient's own request, ie, withdrawal of the consent for treatment.
- If, in the Investigator's opinion, continuation with the administration of IMP would be detrimental to the patient's well-being.
- At the specific request of the Sponsor.

A patient must withdraw from treatment with IMP in either of the following cases:

- Intercurrent condition that requires discontinuation of IMP.
- Pregnancy in female participants.
- Necessity to use prohibited therapy (see Section 6.5)

Any abnormal laboratory value will be immediately rechecked for confirmation before making a decision of permanent discontinuation of the IMP for the concerned patient.

See the SoA for data to be collected at the time of intervention discontinuation and follow-up and for any further evaluations that need to be completed.

Handling of participants after definitive intervention discontinuation

Participants will be followed-up according to the study procedures specified in this protocol up to the scheduled date of study completion, or up to recovery or stabilization of any AE to be followed-up as specified in this protocol, whichever comes last.

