9.3 POPULATIONS FOR ANALYSES

For purposes of analysis, the following populations are defined (Table 6):

Table 6 - Populations for analyses

Population	Description		
ITT	All randomized (patients who signed ICF and with a treatment arm allocated before first IMP and recorded in the IRT database) participants, irrespective of the treatment actually being received, analyzed according to the treatment group allocated by randomization.		
PP	The PP population is a subset of ITT population with no major protocol deviations. Participants included in this population will fulfill at least the criteria below:		
	 randomized and received only the treatment allocated at the randomization 		
	did not permanently discontinue treatment		
	The PP population will be fully defined in the SAP.		
Safety	All randomized participants who received at least one dose of IMP, regardless of the amount of treatment administered. Patients will be analyzed according to the treatment actually received.		

ICF: informed consent form; IRT: interactive response technology; ITT: intent to treat; PP: per protocol; SAP: statistical analysis plan

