2.1.3 Efficacy endpoints

Observation period for efficacy endpoints

The 12–week randomized period for efficacy variables is defined as the time from randomization until Week 12 (Visit 18) for randomized patients, regardless of study treatment discontinuation.

CGM data

A patient is eligible for randomization if a minimum of 10 days (not necessarily consecutive) of useable CGM data are generated during 20 consecutive days at run-in period.

At Week 12, CGM is evaluable if there is at least 10 days of useable CGM data (not necessarily consecutives) within the analysis time windows (see Section 2.5.4) at Week 12 evaluation.

Useable CGM data for a day/a 24-hour CGM profile are defined as having:

- At least 80% time of records per 24 hours (ie, 231 data points among the 288 recorded in 24 hours).
- No gap (missing data) lasting for a total of ≥ 2 hours per 24 hours besides the warm-up time for the sensor after insertion.

For CGM endpoints, details on derivations are available in Section 2.5.

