2.3.1.2 Per-protocol population

The per-protocol population (PP) is a subset of the ITT population which will comprise all randomized patients, who are exposed, who do not permanently discontinued IMP allocated by IRT, who completed the study as per protocol (as reported in the EOS page) and who do not present any major protocol deviations that potentially impact the primary efficacy results, as presented below:

• Major or critical deviation linked to inclusion criteria:

- From inclusion criterion I02: Patients without T1DM.
- From inclusion criterion I03: Not treated with multiple daily injections (MDI) using basal insulin analog once daily and rapid acting insulin analogs for at least one year
- From inclusion criterion I04: HbA1c <7% or >10%
- Major or critical deviation linked to exclusion criteria:
 - With E09: Patients having received basal insulin dose ≥ 0.6 U/kg body weight within 30 days prior to screening.
 - With E13: Patients who will need real time, flash or implantable CGM for routine care any time during study participation.
 - With E23: Inappropriate CGM use during run-in period evidenced by failure to obtain a minimum of 10 days (not necessarily consecutive) of useable CGM data by the end of run-in.
- Other major or critical deviation potentially impacting primary efficacy results:
 - Not taken only the treatment allocated by IRT (ie, wrong treatment taken at randomization or switch during the study)
 - Wrong stratum of randomization
 - Taken any prohibited medications for more than 10 consecutive days during the study as follows:
 - Any glucose-lowering agents other than IMP, the patient's current background basal insulin analog during the run-in period (which may not be changed during the study), or the patient's existing mealtime insulin (which may not be changed during the study). This includes oral or injectable glucose lowering agents, other type of basal insulin (eg, NPH), pre-mixed insulin, and human regular insulin
 - Insulin pump therapy.
 - Systemic glucocorticoids (topical or inhaled applications are allowed).
 - Patient who did not receive the CGM at Week 9, or for whom there are issues with uploading the CGM data at Week 12. This will be evaluated for patients who completed the treatment period and the study

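### The per-protocol definition tolerates 10 consecutive days of any prohibited glucose-lowering therapy, an allowance the protocol gives only to glucocorticoids, and 10 days can be a whole evaluable Week 12 CGM record

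*SAP*

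**What the plan says.** Protocol 6.5 lists what is prohibited during the study. The first item is "Any glucose-lowering agents other than" the study drug, the run-in basal insulin and the existing mealtime insulin. The second reads "Insulin pump therapy is not allowed during the course of the study". Neither carries a duration. Among these classes only the steroid item does: "Systemic glucocorticoids for more than 10 consecutive days (topical or inhaled applications are allowed".

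Protocol 9.3 gives minimum PP criteria and adds "The PP population will be fully defined in the SAP". SAP 2.3.1.2 then lists the deviations that remove a patient. One is "Taken any prohibited medications for more than 10 consecutive days during the study as follows", and its three sub-items are other glucose-lowering agents, pump therapy and systemic glucocorticoids. The duration now stands in the lead-in and governs all three; the steroid sub-item no longer has its own. SAP 1.5, on modifications to the protocol's statistical section, does not mention this, and SAP 1.6 reports none.

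On the endpoint, SAP 2.1.3 says "At Week 12, CGM is evaluable if there is at least 10 days of useable CGM data (not necessarily consecutives". A day is useable if at least 80% of readings are present and there is no gap of 2 hours or more apart from sensor warm-up. Treatment taken on that day plays no part.

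**The concern.** The primary analysis is ITT and uses Week 12 CGM whatever treatment was taken. The PP analysis, the first sensitivity analysis in SAP 2.4.4.1.2, is the planned look at non-inferiority with off-protocol treatment set aside. The trial is open-label, so an investigator may respond to poor control in a way that depends on the arm. If patients whose endpoint was recorded on added glucose-lowering therapy stay in the PP set, that analysis can carry the same distortion as the ITT analysis and cannot reveal it. The number 10 makes this awkward: the longest tolerated run of prohibited therapy is as long as the smallest record that counts as evaluable.

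**Working it through.** **1. The rules side by side.**

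| Class | Protocol 6.5 | Protocol 5.2, before screening | SAP 2.3.1.2, leaves PP if |
|---|---|---|---|
| Other glucose-lowering agents | prohibited, no duration | E 10: any use within 3 months | run longer than 10 days |
| Insulin pump | prohibited, no duration | E 12: any use within 6 months | run longer than 10 days |
| Systemic glucocorticoids | prohibited beyond 10 consecutive days | E 11: more than 10 days within 3 months | run longer than 10 days |

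Both protocol lists reserve the 10-day allowance for steroids.

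**2. Minimum record.** A run of exactly 10 days is not more than 10, so the longest tolerated run is 10 days. The minimum evaluable record is 10 useable days (SAP 2.1.3; Protocol 9.2). Share that can be exposed: 10/10 = 100%. CGM days run from midnight to midnight (SAP 2.5.1) and the device is collected at Visit 18, Day 84, so Day 84 is normally incomplete. Ten days ending on Day 83 are Days 74 to 83 (83 − 74 + 1 = 10). The 100% case also requires that no other recorded day be useable.

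**3. Longer records.** One unbroken 10-day run covers at most 10/20 = 50% of a full 20-day record. Because the rule counts consecutive days, one day off restarts the count. The most exposed days possible in D days without a run above 10 is D − floor(D/11):

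- 20-day recording: 20 − 1 = 19 (95%)
- analysis window, Days 57 to 91 (SAP 2.5.4): 35 − 3 = 32 (91%)
- 84 treatment days: 84 − 7 = 77 (92%)

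These are limits of what the wording permits, not expected patterns. Under the scope in Protocol 6.5, the figure for glucose-lowering agents and pumps would be 0.

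**4. Other routes out of the PP set.** Protocol 7.1.1 makes "Necessity to use prohibited therapy (see Section 6.5" a reason for mandatory withdrawal from study drug, and permanent discontinuation removes a patient from PP. That works only where the drug was in fact stopped for good. SAP 2.3.1.2 also excludes, at any duration, "Not taken only the treatment allocated by IRT (ie, wrong treatment taken at randomization or switch during the study". That may catch a change of basal insulin. It does not clearly catch an oral or injectable agent, or regular or premixed insulin, taken alongside the study drug. Read so broadly that it did, it would leave the separate prohibited-medication item with little to do.

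**5. Scale.** The plan's sample size reproduces: (1.96 + 1.282)² × 1.81 × 14.7² / 5.6² = 131.09, against 131 stated. The margin is 0.1 × 56 = 5.6 points, and the standard error of m1 − 0.9·m0 at 131 per arm is √(1.81 × 14.7²/131) = 1.73 points. The documents give no rate of prohibited use and no effect of it on time in range, so what follows is assumption. If a fraction p of the Toujeo PP patients, and none of the Tresiba patients, gain d points, the contrast moves by p × d:

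- p = 1%, d = 5: 0.05 points (0.05/5.6 = 0.9% of the margin)
- p = 10%, d = 15: 1.5 points (1.5/5.6 = 27% of the margin)

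If the fraction is equal in both arms, the contrast moves by p·d − 0.9·p·d = 0.1·p·d, at most 0.15 points over the same range. Only an imbalance matters, and its sign depends on which arm has the excess.

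**The case against.** The strongest reply is that the two texts do different jobs. Protocol 6.5 governs conduct; SAP 2.3.1.2 picks out the major deviations likely to affect the primary result, and Protocol 9.3 hands that definition to the SAP. Prohibiting a drug does not oblige anyone to exclude every patient who took one dose. This stands as far as it goes: a reader might infer that the SAP breaches the protocol, and the documents do not support that. What does not stand is the particular tolerance, because it ignores when the exposure fell relative to the CGM record.

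A second reply is that withdrawal and the treatment-switch exclusion leave few patients. They do narrow the group to those with add-on therapy who were neither withdrawn nor switched.

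A third is visibility: SAP 2.4.2.2 tabulates concomitant antidiabetic drugs by arm and SAP 2.2 tabulates major deviations. Those tables could show an imbalance in add-on drugs. They would not show whether use fell on CGM days or what it did to the PP estimate.

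A reader might also infer that excluding a patient for a long steroid course in the run-in is misplaced because it is far from the endpoint. It is not: baseline CGM is recorded in Weeks −3 to −1 and baseline time in range is the ANCOVA covariate.

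**Conclusion.** The mismatch in scope and the day counts follow from the text and need no assumption. As written, the PP set can keep a patient with all of a minimum evaluable Week 12 record, or nearly all of a longer one if use is interrupted, recorded on prohibited add-on therapy.

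The consequence is limited. A reader might infer that the non-inferiority conclusion is at risk; it is not, because that decision rests on the ITT analysis, and the sample size is also untouched. Full exposure is the extreme case. The illustrative shift of 0.05 to 1.5 points rests wholly on assumed rates and gains, its upper end stacks a large imbalance on a large gain, and even that is below one standard error of the planned contrast. The effect may be small. The point is worth correcting because it weakens an analysis meant to set off-protocol treatment aside, and the correction is cheap.

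**What to change.** In SAP 2.3.1.2, reconcile the PP rule with Protocol 6.5 by keeping the 10-consecutive-day threshold for systemic glucocorticoids only. For the PP analysis, treat Week 12 CGM days on a prohibited glucose-lowering agent or pump as not useable and re-apply the 10-day minimum. The alternative is to exclude patients with such use on any day contributing to the endpoint. Treat baseline CGM days the same way. If the wider tolerance is kept, state the reason and say how exposure during CGM is handled. No cap on total days of use is proposed, since no figure in the documents supports one. This changes an analysis set, not the list of prohibited therapies.

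Three details need a sentence each:

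- **Partial dates.** SAP 2.5.3 does not impute medication dates. One workable rule counts a CGM day as exposed unless the recorded dates rule it out.
- **Too few days left.** SAP 2.3.1.2 keeps patients with non-evaluable CGM in the PP set, so under the day-level option they would be imputed under missing at random. The SAP should say so.
- **Baseline.** Dropping baseline days could leave a missing baseline with an observed Week 12 value, a pattern SAP 2.4.4.1.1 does not expect but SAP 2.5.3 (Step 1a) can handle. It should not reopen eligibility under E 23.

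The cost is SAP wording and a day-level flag from medication dates that Protocol 6.5 already requires; the existing threshold needs the same dates. The downsides are that a few patients or days leave the PP analysis and that the selection rests on post-randomization use, which may itself be driven by outcome.

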2.3.1.3 Population without trial impact (disruption) due to COVID-19

The "Population without trial impact (disruption) due to COVID-19" is defined as patient without.

- Premature treatment discontinuation due to COVID-19
- Premature end of study due to COVID-19
- Critical or major protocol deviations due to COVID-19

For the primary efficacy endpoint, analysis based on Population without trial impact (disruption) due to COVID-19 will be performed as sensitivity analysis.

2.3.2 Safety population

The safety population is defined as all randomized patients who received at least 1 dose or part of a dose of the IMP. Patients in the safety population will be analyzed according to the actual treatment received. In the event that different treatments are administrated to the same patient, the patient is to be analyzed using the treatment that he/she is on for the most time.

In addition

- Non-randomized but treated patients will not be part of the safety population; however, their safety data will be presented separately
- Randomized patients for whom it is unclear whether they took the IMP will be included in the safety population as randomized

2.4 STATISTICAL METHODS

2.4.1 Demographics and baseline characteristics

Continuous data will be summarized using the number of available data, mean, standard deviation (SD), median, minimum, first quartile (Q1), third quartile (Q3), and maximum for each treatment group.

Categorical and ordinal data will be summarized using the number and percentage of patients in each treatment group.

Parameters will be summarized on the ITT population analyzed in the treatment group to which they were randomized. Analyses for the safety population (respectively, PP population) will be included in the appendices if the size of the safety population (respectively PP population) is different (>10%) from the size of that in the primary analysis population (ie, ITT population) for any treatment group.

Parameters described in Section 2.1.1 will be summarized by treatment group using descriptive statistics.

For medical and surgical history, non-prespecified diagnoses will be summarized by treatment group according to the MedDRA dictionary. Incidence tables will present by SOC and HLT – sorted by SOC internationally agreed order and by decreasing frequency of HLT based on incidence in the overall treatment group – the number (n) and percentage (%) of patients experiencing an event. Multiple occurrences of the same event in the same patient will be counted only once in the tables. The denominator for computation of percentages will be the randomized population within each treatment group.

P-values on demographic and baseline characteristic data will not be calculated.

2.4.2 Prior or concomitant medications

The prior, concomitant and post-treatment medications will be presented for the ITT population separately for anti-diabetic medications and other (ie, non-anti-diabetic) medications.

2.4.2.1 Non-antidiabetic medications

Non antidiabetic medications will be summarized by treatment group according to the WHO-DD dictionary, considering the first digit of the anatomical therapeutic chemical (ATC) class (anatomic category) and the first 3 digits of the ATC class (therapeutic category).

All ATC codes corresponding to a medication will be summarized, and patients will be counted once in each ATC category (anatomic or therapeutic) linked to the medication. Therefore, patients may be counted several times for the same medication.

The table for prior non-antidiabetic medications will be sorted by decreasing frequency of ATC followed by all other therapeutic classes based on the overall incidence across treatment group. In case of equal frequency regarding ATCs (anatomic or therapeutic categories), alphabetical order will be used.

The tables for concomitant and post-treatment medications will be sorted by decreasing frequency of anatomic class followed by therapeutic classes based on the incidence in the Toujeo group. In case of equal frequency regarding ATCs (anatomic or therapeutic categories), alphabetical order will be used.

2.4.2.2 Antidiabetic medications

The table for prior anti-diabetic medications other than basal and mealtime insulin analogs (permitted or not permitted per protocol) will be summarized per pre-defined and standardized medication name based on the overall incidence across treatment group. In case of equal frequency, alphabetical order will be used.

The table for concomitant anti-diabetic medications other than basal and mealtime insulin analogs (permitted or not permitted per protocol) will be summarized per pre-defined and standardized medication name based on the incidence in the Toujeo group. In case of equal frequency, alphabetical order will be used.

The following predefined classes (customised drug grouping [CDG]) will be considered for prior and concomitant:

At least one non-insulin therapy

- Biguanides
- Sulfonylureas
- Glinides
- Thiazolidinedione

- DPP-4 inhibitors
- SGLT-2 inhibitors
- GLP1-RA
- Alpha-glucosidase inhibitors
- Other blood glucose lowering drugs

At least one insulin therapy different from insulin analog (even if not permitted in prior or concomitant)

- Insulin NPH
- Premixed insulin
- Short acting regular human insulin

The table for post anti-diabetic medications will be summarized per pre-defined class and standardized medication name based on the incidence in the Toujeo group. In case of equal frequency, alphabetical order will be used. Insulin therapy could include insulin analog.

A list of codes to be used in determining these pre-defined classes is in a separate operational document.

Of note, basal and mealtime insulin analogs as prior medications are described in Section 2.1.1

Frequency statistics including number of patients and percentage will be provided.

2.4.3 Extent of investigational medicinal product exposure and compliance

The extent of IMP exposure and compliance will be assessed and summarized by actual treatment within the safety population (Section 2.3.2).

2.4.3.1 Extent of investigational medicinal product exposure

The extent of IMP exposure will be assessed by the duration of IMP exposure over the study period.

The duration of treatment exposure will be the total number of days of administration of the open-label IMP, regardless of unplanned intermittent discontinuations (see Section 2.5.3 for calculation in case of missing or incomplete data). The duration of IMP exposure will be calculated as:

• (date of the last open-label IMP injection – date of the first open-label IMP injection) + 1.

Duration of IMP exposure will be summarized descriptively as a quantitative variable (number, mean, SD, median, minimum, and maximum). In addition, duration of treatment exposure will also be summarized categorically by numbers and percentages for each of the following categories and cumulatively according to these categories 1 to 21 days, 22 to 42 days, 43 to 63 days, 64 to 84 days and >84 days.

Additionally, the cumulative duration of treatment exposure will be provided, defined as the sum of the duration of treatment exposure for all patients, and will be expressed in patient years.

